5.2. Criteria for eliminating data from Analysis Sets

Elimination codes are used to identify subjects to be eliminated from analysis. Detail is provided below for each set.

5.2.1. Elimination from ITTS

Code 1030 (Study vaccine not administered at all) for all subjects except those from the infectivity control group and code 900 (invalid informed consent or fraud data) will be used for identifying subjects eliminated from ITTS.

5.2.2. Elimination from the Solicited Safety Set

Code 1030 (study vaccine not administered at all), code 900 (invalid informed consent or fraud data) and code 1160 (no post-vaccination solicited safety data) will be used for identifying subjects eliminated from the solicited safety set.

5.2.3. Elimination from the PPS for analysis of immunogenicity and efficacy**5.2.3.1. Excluded subjects**

A subject will be excluded from the PPS analysis of immunogenicity and efficacy analysis under the following conditions

Code	Condition under which the code is used
900	Invalid informed consent or fraud data
1030	Study vaccine not administered at all
1040	Administration of concomitant vaccine(s) forbidden in the protocol 
 • Any investigational or non-registered vaccine other than the study vaccines used during the study period. • A vaccine not foreseen by the study protocol administered during the period starting seven days before each dose and ending seven days after each dose of vaccines administration.
1070	Vaccination not according to protocol 
 • Incomplete vaccination course before treatment withdrawal or subject study conclusion. • Administration not according to protocol for reason specified by the investigator, other than side, site and route. • Wrong replacement or study vaccine administered (not compatible with the vaccine regimen associated to the treatment number). • Study vaccine RTS,S/AS01 not prepared as per protocol

Code	Condition under which the code is used
1080	Good Manufacturing Practice No-Go: Vaccine temperature deviation
1090	Expired vaccine administered
2010	Protocol violation (inclusion/exclusion criteria) 
 Eligibility criteria not met with an impact on immunogenicity data
2040	Administration of any medication forbidden by the protocol which may influence the efficacy endpoints 
 Any investigational or non-registered product drug other than the study vaccines used during the study period. Immunosuppressants or other immune-modifying drugs administered chronically (i.e. more than 14 days in total) during the study period. For corticosteroids, this will mean prednisone \geq 20 mg/day (for adult subjects), or equivalent. Inhaled and topical steroids are allowed. Long-acting immune-modifying drugs administered at any time during the study period (e.g. infliximab). Immunoglobulins and/or any blood products administered during the study period. Drugs known to have anti-Plasmodium properties, used during the challenge period before identification of parasitemia.
2050	Underlying medical condition forbidden by the protocol which may influence the efficacy endpoints
2080	Subjects did not comply with vaccination schedule (See Table 1 , Table 2 , Table 3)
2090	Subjects did not comply with blood sampling schedule (See Table 1 , Table 2 , Table 3)
2100	Serological results not available for anti-CS at all post-vaccination visits
2120	Obvious incoherence or abnormality or error in immunogenicity (antibody) data
3000	Subject did not undergo challenge

5.2.4. Elimination from the Adapted PPS for analysis of efficacy**5.2.4.1. Excluded subjects**

A subject will be excluded from the Adapted PPS analysis of efficacy analysis under the following conditions:

Code	Condition under which the code is used
900	Invalid informed consent or fraud data
1030	Study vaccine not administered at all
1070	Vaccination not according to protocol 
 • Incomplete vaccination course before treatment withdrawal or subject study conclusion. • Administration not according to protocol for reason specified by the investigator, other than side, site and route. • Wrong replacement or study vaccine administered (not compatible with the vaccine regimen associated to the treatment number). • Study vaccine RTS,S/AS01 not prepared as per protocol
3000	Subject did not undergo challenge

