5.3. Exclusion criteria for enrolment

Deviations from exclusion criteria are not allowed because they can potentially jeopardize the scientific integrity of the study, regulatory acceptability or subject safety. Therefore, adherence to the criteria as specified in the protocol is essential.

The following criteria should be checked at the time of study entry. If ANY exclusion criterion applies, the subject must not be included in the study:

- Use of any investigational or non-registered product (drug or vaccine) other than the study vaccines during the period starting 30 days before the first dose of study vaccines (Day -29 to Day 0), or planned use during the study period.
- Any medical condition that in the judgment of the investigator would make intramuscular (IM) injection unsafe.
- Chronic administration (defined as more than 14 days in total) of immunosuppressants or other immune-modifying drugs during the period starting six months prior to the first vaccine dose. For corticosteroids, this will mean prednisone ≥ 20 mg/day (for adult subjects), or equivalent. Inhaled and topical steroids are allowed.
- Administration of long-acting immune-modifying drugs at any time during the study period (e.g. infliximab).
- Chronic use of antibiotics with antimalarial effects (e.g. tetracyclines for dermatologic patients, sulfa for recurrent urinary tract infections, etc.).
- Planned administration/administration of a vaccine not foreseen by the study protocol in the period starting seven days before the first dose.

- Concurrently participating in another clinical study, at any time during the study period, in which the subject has been or will be exposed to an investigational or a non-investigational vaccine/product (pharmaceutical product or device).
- Seropositive for HBsAg or HCV.
- Documented HIV-positive subject.
- Previous vaccination against malaria.
- History of malaria chemoprophylaxis within 60 days prior to vaccination.
- Any history of malaria (for the vaccine groups).
- Planned travel to malaria endemic areas during the study period.
- History of splenectomy.
- Any confirmed or suspected immunosuppressive or immunodeficient condition, based on medical history and physical examination.
- Family history of congenital or hereditary immunodeficiency.
- History of any reaction or hypersensitivity likely to be exacerbated by any component of the vaccine.
- History of anaphylaxis post-vaccination.
- Hypersensitivity to latex.

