7.6.1. Recording of concomitant medications/products and concomitant vaccinations

The following concomitant medication(s)/product(s)/vaccine(s) must be recorded in the eCRF.

- All concomitant medications/products, except vitamins and dietary supplements, administered during the period starting within seven days following each dose of study vaccines (Day 0 to Day 6) and during the entire sporozoite challenge (Day 286 to Day 314).
- Any concomitant vaccination administered in the period starting seven days before the first dose of study vaccines and ending at the last study visit (Day -7 to Day 376) and during the entire sporozoite challenge (Day 286 to Day 314).
- Prophylactic medication (i.e. medication administered in the absence of ANY symptom and in anticipation of a reaction to the vaccination).

E.g. an anti-pyretic is considered to be prophylactic when it is given in the absence of fever and any other symptom, to prevent fever from occurring (fever is defined as temperature $\geq 37.5^{\circ}\text{C}/99.5^{\circ}\text{F}$ for oral, axillary or tympanic route, or $\geq 38.0^{\circ}\text{C}/100.4^{\circ}\text{F}$ for rectal route).

- Any concomitant medications/products/vaccines listed in Section 7.6.2.
- Any concomitant medications/products/vaccines relevant to a SAE/pIMD to be reported as per protocol or administered at any time during the study period for the treatment of a SAE /pIMD. In addition, concomitant medications relevant to SAEs and pIMD need to be recorded on the expedited Adverse Event report.

7.6.2. Concomitant medications/products/vaccines that may lead to the elimination of a subject from ATP analyses

The use of the following concomitant medications/products/vaccines will not require withdrawal of the subject from the study but may determine a subject's evaluability in the ATP analysis. See Section 11.5 for cohorts to be analyzed.

- Any investigational or non-registered product (drug or vaccine) other than the study vaccines used during the study period.
- Immunosuppressants or other immune-modifying drugs administered chronically (i.e. more than 14 days in total) during the study period. For corticosteroids, this will mean prednisone ≥ 20 mg/day (for adult subjects), or equivalent. Inhaled and topical steroids are allowed.

- Long-acting immune-modifying drugs administered at any time during the study period (e.g. infliximab).

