5.1.3. Solicited Safety Set

The solicited Safety Set will include all subjects who received at least one dose of study vaccine and had solicited safety data.

5.1.4. Per-Protocol Set for analysis of immunogenicity and efficacy (PPS for analysis of immunogenicity and efficacy)

The PPS for analysis of immunogenicity and efficacy will include all subjects included in the ITTS who fulfilled all eligibility criteria and received all vaccinations according to protocol procedures within the protocol specified intervals, did not use any medication, vaccine or blood products forbidden by the protocol, did not report any underlying medical condition influencing the efficacy response, had available data concerning immunogenicity endpoint measures, and underwent *P. falciparum* challenge. This will include subjects for whom assay results are available for antibodies against at least one study vaccine antigen after vaccination.

5.1.5. Adapted Per-Protocol Set for analysis of efficacy (Adapted PPS for analysis of efficacy)

The Adapted PPS for analysis of efficacy will include all subjects included in the ITTS who fulfilled all eligibility criteria and received all vaccinations according to protocol procedures within the protocol specified intervals and underwent *P. falciparum* challenge.

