8. CONDUCT OF ANALYSES

8.1. Sequence of analyses

The analyses will be performed stepwise:

- An interim analysis to allow an internal decision for the choice of the booster dose in study Malaria-102 will be performed as soon as the results of the challenge phase will be available on data as clean as possible. This analysis will be descriptive and performed on the Adapted PPS for analysis of efficacy.
- When all the remaining data up to Day 376 will be available, the main analysis will be performed. An integrated study report will be written.

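### The Adapted PPS code list omits two conditions of the set's own definition and has no antimalarial exclusion, so the interim VE is computed on a set other than the one described

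*SAP*

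**What the plan says.** SAP 5.1.5 defines the Adapted PPS as ITTS subjects who "fulfilled all eligibility criteria and received all vaccinations according to protocol procedures within the protocol specified intervals and underwent" the challenge. It sets no condition on medication. SAP 5.2 says that elimination codes identify who is removed, with details given for each set. For the Adapted PPS, SAP 5.2.4.1 states "A subject will be excluded from the Adapted PPS analysis of efficacy analysis under the following conditions" and lists four codes: 900 (invalid consent or fraud), 1030 (no study vaccine given), 1070 (vaccination not according to protocol) and 3000 (not challenged).

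The main PPS list in SAP 5.2.3.1 is longer. It includes:

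- code 2010, worded "Eligibility criteria not met with an impact on immunogenicity data";
- code 2080, for departures from the vaccination schedule;
- code 2040, whose last item is anti-Plasmodium drugs "used during the challenge period before identification of parasitemia".

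SAP 8.1 plans "An interim analysis to allow an internal decision for the choice of the booster dose in study Malaria-102" on the Adapted PPS and calls it descriptive. SAP 8.2 keeps the main objective for the main PPS at study end and warns that results may differ. SAP 6.3.2.2 censors time to onset at the start of antimalarial treatment. For the relative risk it treats everyone in the set as at risk and applies no censoring for incomplete follow-up.

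At entry, Protocol 5.3 excludes chronic use of antibiotics with antimalarial effects, and also "History of malaria chemoprophylaxis within 60 days prior to vaccination".

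**The concern.** A definition and its code list should select the same people. Here a programmer working from 5.2.4.1 would keep subjects whom 5.1.5 rules out, in the analysis that informs a decision about another study. SAP section 9 says the Adapted PPS was created to bring the interim as close as possible to the main analysis, and the omission works against that aim.

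Antimalarial use is a separate weakness, because 5.1.5 contains no medication condition to breach. The main PPS removes anti-Plasmodium drug use during challenge because it may influence the efficacy endpoints. The same reasoning applies to the interim VE, which has the same outcome. Without that code, a negative slide produced by a drug is read as a negative slide produced by the vaccine.

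The main PPS has a smaller gap of its own. Its definition (SAP 5.1.4) requires all eligibility criteria, but code 2010 acts only on failures that bear on immunogenicity. Read literally, a failure that bears only on infection stays in the primary analysis.

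**Working it through.** **Conditions against codes**

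| Condition for the Adapted PPS (SAP 5.1.5) | Code that would enforce it | In 5.2.4.1? |
|---|---|---|
| In the ITTS | 900, 1030 | yes |
| All eligibility criteria met | 2010 | no |
| Vaccinations according to procedure | 1070 | yes |
| Vaccinations within the intervals | 2080 | no |
| Challenged | 3000 | yes |

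None of the items under code 1070 names timing, and the main PPS list gives timing its own code. Two conditions are therefore not enforced. Both missing codes already exist, and neither needs serology.

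**Code 2010 in the main PPS.** The definition asks for all criteria, while the code asks for an immunogenicity impact. The chemoprophylaxis and chronic-antibiotic criteria concern infection, so the code as worded need not remove a breach of either.

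**Size.** Inputs: 19/20 controls and 6/20 vaccinees infected (Protocol 11.4); VE = 100 × (1 − relative risk) (SAP 6.3.1). The numbers of affected subjects below are assumptions. I also assume that the interim VE follows the relative-risk rules of SAP 6.3.2.2, which are written for the main PPS.

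- Plan's own figure: 1 − (6/20)/(19/20) = 1 − 0.300/0.950 = 68.4%, against the stated approximate 68%.
- One ineligible or off-schedule vaccinee kept as a 21st subject: slide-positive, 1 − (7/21)/(19/20) = 64.9%; slide-negative, 1 − (6/21)/(19/20) = 69.9%. The direction is not fixed.
- One vaccinee who would have been infected but was drug-suppressed: 1 − (5/20)/(19/20) = 73.7%, a rise of 5.3 points. With two or three such subjects, VE reads 78.9% (4/20) or 84.2% (3/20).
- One drug-suppressed control: 1 − (6/20)/(18/20) = 66.7%.

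The 5.3 points assume that the drug-taker would have been infected. If one vaccinee in 20 takes such a drug regardless of susceptibility, expected infections are 19 × 0.30 = 5.7, and VE is 1 − (5.7/20)/0.95 = 70.0%. Eliminating that subject gives 1 − (5.7/19)/0.95 = 68.4%. Elimination thus removes the bias on average. In the particular 5/20 case it gives 1 − (5/19)/0.95 = 72.3%, because the suppressed infection itself cannot be recovered.

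**Effect on ranking.** A simulation took five equally effective groups (30% infected, 20 each, ties broken at random). A given group ranks best 20% of the time with no suppressed infection, and 34%, 49% or 65% of the time with one, two or three. Fisher's test of 5/20 against 6/20 gives p = 1.00. This matters only if the booster choice follows the ranking, which the documents do not say.

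**The case against.** The strongest reply is that the interim is descriptive, the primary objective is analysed on a PPS that carries codes 2010, 2040 and 2080, and the SAP itself warns that the two results may differ. That stands: the Adapted PPS list does not touch the primary result. It does not excuse a set that differs from its own definition.

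A second reply is that 1070 is broad enough to catch off-schedule doses. That would depend on what the investigator specifies, and the main PPS treats timing under a separate code.

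A reader might also go further than the documents allow, in four ways:

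- **That every retained subject counts as protected.** Ineligible and off-schedule subjects are scored by their slide result. Only drug-suppressed negatives push a vaccine group's VE upwards. A suppressed control lowers VE in every group and cannot change the ranking.
- **That antimalarial use is screened only from Day 286.** Entry criteria screen earlier use, and planned travel to endemic areas is excluded. The other items of code 2040 cover the whole study period.
- **That a drug taken shortly before challenge goes unrecorded.** Protocol 7.6 has the investigator ask about medication at each visit. Tables 6 to 8 mark eCRF recording at the scheduled visits, including Visits 10 and 11 for vaccinees and Visits 1b and 11 for controls. Protocol 7.6.1, by contrast, requires general recording only on Days 0 to 6 after each dose and Days 286 to 314. This is a conflict to reconcile; it does not prove that data are absent.
- **That a 60-day antimalarial look-back should be tied to challenge.** The documents give no basis for moving that window, and doing so would change the protocol.

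For controls, the chemoprophylaxis criterion does lack an anchor, since they are never vaccinated. However, their criteria are checked again on the day of challenge (Table 8), and their challenge epoch starts at screening (Protocol section 3). The gap is therefore one of wording.

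**Conclusion.** The mismatch between SAP 5.1.5 and 5.2.4.1 is certain and rests on the text alone: eligibility and vaccination intervals are conditions of the set, and no listed code clearly enforces either. The effect on the interim VE has no fixed direction. In the design case, one retained subject gives 64.9% or 69.9% against 68.4%.

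The missing antimalarial exclusion is a second, separate weakness with a known direction among vaccinees. One affected subject in 20 raises that group's VE by 5.3 points if that subject would have been infected, and by 1.6 points on average (70.0% against 68.4%). Both figures assume the design rates and 20 challenged per group. The documents give no count of affected subjects, and it may be zero.

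For the main PPS, the finding is limited to code 2010 being narrower than the definition. The documents do not show how often that would matter, so a reader should not infer that the primary VE is biased.

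**What to change.** In SAP 5.2.4.1, add codes 2010, 2080 and the anti-Plasmodium part of 2040, and add the matching medication condition to 5.1.5. Reword 2010 to cover an impact on immunogenicity or efficacy. That is still narrower than requiring all criteria, so 5.1.4 and 5.1.5 should say that failures bearing on neither are kept.

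In the protocol, reconcile the recording windows in 7.6.1 with the visit-by-visit recording in 7.6 and Tables 6 to 8. Clarify how the chemoprophylaxis criterion in 5.3, worded relative to vaccination, applies to infectivity controls.

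The SAP changes are wording only and use existing codes. The protocol items need a clarification of text. The downside is that a few subjects may be eliminated from the interim set.

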5.3. Important protocol deviations not leading to elimination from per-protocol analysis set

Important protocol deviations not leading to elimination from PPS are defined in MALARIA-092 (205081) Protocol Deviation Management Plan.

PPD

(MALARIA-092 (205081) Protocol Deviation Management Plan)

6. STATISTICAL ANALYSES

Note that standard data derivation rules and statistical methods are described in Annex 1 and will not be repeated below.

6.1. Demography

6.1.1. Analysis of demographics/baseline characteristics planned in the protocol

A study flow table (consort) will be generated to present the number of subjects screened, randomized, receiving doses and included in the PPS for analyses.

The analysis of demographics will be performed on the ITTS and on the PPS for analysis of immunogenicity and efficacy.

Demographic characteristics (age at first vaccination in years for the vaccinated groups and at the time of the screening for the control group, gender, and race) will be summarized by group and overall using descriptive statistics:

- Frequency tables will be generated for categorical variables such as race.
- Mean, median, standard deviation (SD) and range will be provided for continuous data such as age.

Withdrawal status will be summarized by group using descriptive statistics:

- The number of subjects enrolled into the study as well as the number of subjects excluded from PPS for analyses will be tabulated.
- The number of withdrawn subjects will be tabulated according to the reason for withdrawal.

6.2. Exposure

6.2.1. Analysis of exposure planned in the protocol

The number and percentages of subjects with vaccination will be summarized overall and by group for all groups where a vaccination is part of the study procedure. The analysis of exposure will be performed on the ITTS.

6.3. Efficacy analysis

6.3.1. Analysis of efficacy planned in the protocol

The analysis of efficacy will be performed on the PPS for analysis of immunogenicity and efficacy.

Efficacy will be assessed by comparison of *P. falciparum* parasitemia incidence and time to onset of *P. falciparum* parasitemia after sporozoite challenge.

Vaccine efficacy (VE) is defined as $100 \times (1 - \text{Relative Risk})$. Relative risk of infection and 95% CI will be calculated.

Fisher's Exact test will be used for the comparison of *P. falciparum* parasitemia incidence after challenge between each one of the vaccine groups (AduFx, 2PedFx, PedFx, Adu2Fx, and Adu1Fx) and the infectivity control group.

Kaplan-Meier analysis will be performed on time to onset of *P. falciparum* parasitemia, for comparisons between each one of the vaccine groups (AduFx, 2PedFx, PedFx, Adu2Fx, and Adu1Fx) and the infectivity control group, using the log-rank statistic.

The same methodology will be applied for the evaluation of the vaccinated groups versus the immunization schedule of reference (AduFx group).

All statistical tests will be two-tailed at 5% significance level.

6.3.2. Additional considerations

6.3.2.1. Case definition

The primary case definition of *P. falciparum* infection is an asexual blood stage *P. falciparum* parasite density > 0 detected by blood slide reading.

6.3.2.2. Risk periods

For the analyses of time to onset of parasitemia (Kaplan-Meier and Log-Rank), time at risk will start on first day of challenge. Time at risk will be censored on protocol visit D314 (28 days post challenge), drop-out date, start date of antimalarial treatment or date meeting an endpoint, whichever occurs first. Time at risk will be calculated as: censor date – date challenge + 1.

For the analysis of proportion affected (relative risk), all subjects included in the PPS for analysis of immunogenicity and efficacy will be considered at risk of infection and no censoring or elimination will be applied for subjects not completing the entire protocol defined post challenge follow-up (visit D314 - 28 days post challenge).

